4 SAFETY ASSESSMENT

4.1 Adverse Events

4.1.1 Definition of Adverse Events

As defined by the International Conference on Harmonisation of Technical Requirements for Registration of Pharmaceuticals for Human Use (ICH), an AE is:

Any untoward medical occurrence in a patient or clinical investigations subject administered a pharmaceutical product and which does not necessarily have to have a causal relationship with this treatment.

An AE can therefore be any unfavorable and unintended sign (including an abnormal laboratory finding), symptom, or disease temporally associated with the use of a medicinal product, whether or not considered related to the medicinal product.

An AE includes but is not limited to:

- Any clinically significant worsening of a pre-existing condition;
- An AE occurring from overdose (ie, a dose higher than that prescribed by a healthcare professional for clinical reasons, or a dose higher than that described on the marketed product label) of an investigational or marketed product, whether accidental or intentional;
- An AE occurring from abuse (eg, use for non-clinical reasons) of an investigational or marketed product;
- An AE that has been associated with the discontinuation of the use of an investigational or marketed product; and
- Adverse changes from baseline, which are listed in the National Cancer Institute's Common Terminology Criteria for Adverse Events Version 3.0 (NCI CTCAE V3.0), which can be found in Attachment 1.

A protocol-related AE is an AE occurring during a clinical trial that is not related to the investigational product, but is considered by the Investigator or Medical Monitor (or designee) to be related to the research conditions, ie, related to the fact that a subject is participating in the study. For example, a protocol-related AE may be an untoward event occurring during a washout period or an event related to a medical procedure required by the protocol.

4.1.2 Study Reporting Period for Adverse Events

The reporting period for adverse events is the period from the signing of informed consent through Study Day 350. AEs will not be recorded for patients deemed screening failures.

4.1.3 Recording of Adverse Events

AEs will be reported using a recognized medical term or diagnosis that accurately reflects the event. AEs will be assessed by the investigator for severity, relationship to the investigational study product, possible etiologies and whether the event meets criteria as a SAE and therefore requires immediate notification of the Sponsor. See Sections 4.3 and 4.4 regarding guidelines

for assessment of severity and relationship, respectively, and Section 4.2.1 for the definition of SAEs. If an AE evolves into a condition which becomes “serious” the investigator will additionally report to the Sponsor on the **SERIOUS ADVERSE EVENT (SAE) REPORT FORM**.

4.2 Serious Adverse Events

4.2.1 Definition of Serious Adverse Events

A Serious Adverse Event (SAE) is any AE that:

- Results in death;
- Is life-threatening;
 - This term refers to an event in which the subject was at risk of death at the time of the event; it does not refer to an event that hypothetically might have caused death if it were more severe.
- Requires inpatient hospitalization or prolongation of existing hospitalization;
 - In general, hospitalization signifies that the subject has been detained (usually involving at least an overnight stay) at the hospital or emergency ward for observation and/or treatment that would not have been appropriate in an outpatient setting. Complications that occur during hospitalization are AEs. If a complication prolongs hospitalization or fulfills any other serious criteria, the event is serious. When in doubt as to whether “hospitalization” occurred or was necessary, the AE should be considered serious. Hospitalization for elective treatment of a pre-existing condition that did not worsen from baseline is not considered an AE.
- Results in persistent or significant disability/incapacity; or
 - The term disability means a substantial disruption of a person’s ability to conduct normal life functions. This definition is not intended to include experiences of relatively minor medical significance such as uncomplicated headache, nausea, vomiting, diarrhea, influenza, and accidental trauma (eg, sprained ankle) which may interfere or prevent everyday life functions but do not constitute a substantial disruption.
- Is a congenital anomaly/birth defect in offspring of the subject.
- Medically important events.
 - Medical or scientific judgment should be exercised in deciding whether (expedited) reporting is appropriate in other situations, such as important medical events that may not be immediately life-threatening or result in death or hospitalization but may jeopardize the subject or may require medical or surgical intervention to prevent one of the other outcomes listed in the above definition. These events should also be considered serious. Examples of medically important events are intensive treatment in an emergency room or at home for allergic bronchospasm; blood dyscrasias or convulsions that do not result in hospitalizations; or development of drug dependency or drug abuse.

4.2.2 Study Reporting Period for Serious Adverse Events

The reporting period for SAEs is the period from the signing of informed consent through Study Day 350. SAEs will also be recorded for patients deemed screening failures. SAEs must be followed until resolution by the investigator, even if this extends beyond the study reporting period. Resolution of an SAE is defined as the return to baseline status or stabilization of the condition with the expectation that it will remain chronic.

At any time after completion of the study, if an investigator becomes aware of an SAE that is suspected by the investigator to be related to study product, the event should be reported to MedImmune Product Safety.

4.2.3 Notification of Sponsor of Serious Adverse Events

Within 24 hours of identifying a Serious Adverse Event, regardless of the presumed relationship to the Study Drug, the investigator must complete the *SERIOUS ADVERSE EVENT (SAE) REPORT FORM* and Safety Fax Notification Cover Page, and fax to MedImmune Product Safety.

Note: Provide all available information at the time of form completion. When additional information becomes available, submit a follow-up ***SERIOUS ADVERSE EVENT (SAE) REPORT FORM*** with the new information. Investigators should not wait to collect additional information to fully document the event before notifying MedImmune of a serious adverse event.

MedImmune contact information:

Product Safety
MedImmune

Fax: [REDACTED]

MedImmune, as Sponsor of the study being conducted under an Investigational New Drug Application (IND), is responsible for reporting certain SAEs as IND safety reports to the Food and Drug Administration (FDA), other applicable regulatory authorities, and participating investigators, in accordance with the U.S. Code of Federal Regulations (21 CFR 312.32 and 312.33) ICH Guidelines, and/or local regulatory requirements. MedImmune may be required to report certain SAEs to regulatory authorities within 7 calendar days of being notified about the event; therefore, it is important that investigators submit additional information requested by MedImmune as soon as it becomes available.

4.2.4 Notification of Institutional Review Board or Independent Ethics Committee of Serious Adverse Events

The investigator must comply with the applicable regulatory requirements related to the reporting of serious adverse events to the Institutional Review Board or Independent Ethics Committee. The Institutional Review Board or Independent Ethics Committee must be informed in a timely manner by the principal investigator of serious adverse events occurring at their site during the study. Investigators must also submit safety information provided by MedImmune to the Institutional Review Board or Independent Ethics Committee as detailed in Section 7.2.

4.2.5 Recording of Serious Adverse Events

SAEs will be recorded on the ***SERIOUS ADVERSE EVENT (SAE) REPORT FORM*** using a recognized medical term or diagnosis that accurately reflects the event. SAEs will be assessed

by the investigator for severity, relationship to the study product and possible etiologies. See Sections 4.3 and 4.4 regarding guidelines for assessment of severity and relationship, respectively. For the purpose of study analysis, if the event has not resolved at the end of the study reporting period it will be documented as ongoing. For purposes of regulatory safety monitoring the investigator is required to follow the event to resolution and report to the Sponsor the outcome of the event using the **SERIOUS ADVERSE EVENT (SAE) REPORT FORM**.

4.3 Assessment of Severity

Assessment of severity is one of the responsibilities of the investigator in the evaluation of adverse events and serious adverse events. The determination of severity should be made by a health care professional qualified to review AE information, provide a medical evaluation of AEs, and classify AEs based upon medical judgment and the severity categories of *Grade 1, Grade 2, Grade 3, Grade 4, and Grade 5*. Severity of toxicity will be graded according to the NCI CTCAE V3.0, as described in detail in Attachment 1.

4.4 Assessment of Relationship

An SAE is considered “product-related” for the purposes of regulatory reporting if the Investigator, the Medical Monitor, or the Product Safety Physician assesses the SAE as possibly, probably, or definitely related to study drug. This is not a conclusive determination of causal association between the product and the event. Whenever the Investigator’s assessment is unknown or unclear, the SAE is treated as product-related for the purposes of reporting to regulatory authorities. An SAE may be deemed to be not related to the product for purposes of regulatory reporting only if the Investigator, Medical Monitor, and Product Safety Physician, if applicable, agree that the SAE is not product-related.

The investigator is required to provide an assessment of relationship of AEs and SAEs to the study product. A number of factors should be considered in making this assessment including: 1) the temporal relationship of the event to the administration of study product; 2) whether an alternative etiology has been identified; and 3) biological plausibility. The following guidelines should be used by investigators to assess the relationship of an AE to study product administration.

Relationship assessments that indicate an “Unlikely Relationship” to study product:

None: The event is related to an etiology other than the study product (the alternative etiology must be documented in the study subject’s medical record).

Remote: The event is unlikely to be related to the study product and likely to be related to factors other than study product.

Relationship assessments that indicate a “Likely Relationship” to study product:

Possible: There is an association between the event and the administration of the study product and there is a plausible mechanism for the event to be related to study

product; but there may also be alternative etiology, such as characteristics of the subject's clinical status or underlying disease.

Probable: There is an association between the event and the administration of study product, a plausible mechanism for the event to be related to the study product and the event could not be reasonably explained by known characteristics of the subject's clinical status or an alternative etiology is not apparent.

Definite: There is an association between the event and the administration of study product, a plausible mechanism for the event to be related to the study product and causes other than the study product have been ruled out and/or the event re-appeared on re-exposure to the study product.

4.5 Other Events Requiring Immediate Reporting

In addition to SAEs, the following events must be reported *within 24 hours* by fax to MedImmune Product Safety:

1. Any withdrawal of consent during the study
2. Pregnancy or intent to become pregnant. Patients who wish to become pregnant should be followed 3 months after the last dose of study drug*
3. Hypersensitivity (anaphylactic) reaction to the study drug, Grade 1 or higher
4. Infusion reaction, Grade 1 or higher
5. Severe viral infection, Grade 3 or higher
6. Any event which, in the opinion of the investigator or the Medical Monitor, contraindicates further dosing such as illnesses or complications.

*Patients who become pregnant during the study period must not receive additional doses of study product and should proceed to the follow-up phase within 2 weeks of a positive pregnancy test or making the decision to become pregnant. The follow-up phase will start with the procedures scheduled for Study Day 185 and will end on Study Day 350. Patients who become pregnant during the follow-up period should continue the follow-up phase through Study Day 350. A pregnancy should be followed for outcome, any premature terminations reported, and the health status of the mother and child including date of delivery and the child's gender and weight should be reported to MedImmune Product Safety after delivery.

4.6 Safety Management During the Study

The MedImmune Medical Monitor has primary responsibility for the ongoing medical review of safety data throughout the study. This includes immediate review of SAEs and timely review of other AEs reported during the study. The MedImmune Product Safety Monitor has responsibility for the receipt, review, investigation, and follow-up of SAEs reported by the clinical study sites.

The SMC will independently review cumulative safety surveillance data, as well as the decisions of the Medical Monitor regarding dose escalation, on a regular basis throughout the study and make recommendations regarding further conduct of the study. The SMC will also review safety data at other time points in response to AEs felt to be medically significant by the Medical Monitor. The SMC is composed of at least two MedImmune physicians who are not directly

involved in the day to day operations of the study, and at least two physicians who are not employees of MedImmune.

4.7 Interruption or Discontinuation of Study Dosing in Individual Patients

An individual patient will not receive any further study drug if any of the following occur in the patient in question:

- Withdrawal of consent;
- Pregnancy (Patients who become pregnant during the study period must not receive additional doses of study drug and should proceed to the follow-up phase within 2 weeks of a positive pregnancy test or making the decision to become pregnant. The follow-up phase will start with the procedures scheduled for Study Day 185 and will end on Study Day 350);
- Any life-threatening clinical event related to the study drug;
- Severe hypersensitivity (anaphylactic) reaction to the study drug, Grade 3 or higher;
- Infusion reactions, Grade 3 or higher as defined in Table 3;
- Serious clinical infections with a virus of the herpes family (including disseminated herpes infection, herpes encephalitis, or ophthalmic herpes infection) or with CMV or EBV;
- If 3 consecutive doses of study drug are missed due to abnormal LFTs (ALT, AST);
- Two consecutive total bilirubin values taken at least 1 week apart $> 2 \times$ ULN not due to Gilbert's syndrome or hemolysis; or
- Any event that, in the opinion of the investigator or the Medical Monitor, contraindicates further dosing such as illnesses or complications.

Patients who are permanently discontinued from study drug for any of these reasons, with the exception of withdrawal of consent, will be followed for the full study period (through Study Day 350), including the collection of any mandated blood and urine specimens.

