3.4.4.2 Dose Modification for Toxicity Management: Blood Chemistry Abnormalities

If total bilirubin is $> 2 \times \text{ULN}$ at the central laboratory:

- Do not administer study drug at next dosing visit.
- Repeat total bilirubin as well as direct and indirect values, liver function tests (LFTs; including AST, ALT, and alkaline phosphatase), evaluate reticulocyte count immediately to confirm abnormalities. Repeat all tests again in 1 week.
 - If bilirubin remains $> 2 \times \text{ULN}$ (not due to Gilbert's syndrome or hemolysis) do not administer study drug at next dosing visit
 - If bilirubin returns to within normal limits ($< \text{ULN}$), study drug may be administered at next scheduled dosing visit
 - If repeat bilirubin is $< 2 \times \text{ULN}$ but $> \text{ULN}$; hold dose and discuss with medical monitor.

Study drug will be discontinued in subjects who miss 2 consecutive scheduled doses of study drug due to elevated bilirubin (see section 4.7).

If ALT or AST is $> 3 \times \text{ULN}$, refer to Guidance for Abnormal Liver Function Tests in Appendix J.

Study drug will be discontinued in subjects who miss 3 consecutive scheduled doses of study drug due to elevated ALT or AST (see 4.7).

As indicated in the Guidance for Abnormal Liver Function Tests (Appendix J), additional laboratory tests may be ordered from Quintiles Laboratory as needed. The LFTs that the guidelines require to be repeated are AST, ALT, total bilirubin and alkaline phosphatase.

Additional tests may be ordered as required by investigators, these tests include: CPK, GGT, INR, PT, albumin, EBV, CMV, hepatitis A antibody, hepatitis B surface antigen, hepatitis B core antibody and hepatitis C antibody.

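### The permanent bilirubin stop in Section 3.4.4.2 does not match Section 4.7, which it cites, so a site working from 3.4.4.2 could re-dose a patient whom 4.7 bars

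*Protocol*

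**What the plan says.** Section 3.4.4.2 of the protocol starts from a central-laboratory total bilirubin above 2 × ULN. The next dose is withheld and the tests are repeated at once, followed by a further check: "Repeat all tests again in 1 week". Three results are then distinguished:

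- Still above 2 × ULN: "not due to Gilbert's syndrome or hemolysis) do not administer study drug at next dosing visit".
- Back below ULN: drug may be given at the next scheduled visit.
- Between ULN and 2 × ULN: "hold dose and discuss with medical monitor".

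The permanent stop follows as a separate sentence: "Study drug will be discontinued in subjects who miss 2 consecutive scheduled doses of study drug due to elevated bilirubin (see section 4.7").

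Section 4.7 opens with "An individual patient will not receive any further study drug if any of the following occur in the patient in question". Its bilirubin entry is "Two consecutive total bilirubin values taken at least 1 week apart" above 2 × ULN, "not due to Gilbert's syndrome or hemolysis". It has no entry that counts doses missed because of bilirubin. Its transaminase entry does count missed doses: "If 3 consecutive doses of study drug are missed due to abnormal LFTs (ALT, AST"). That agrees with the transaminase sentence in 3.4.4.2.

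**The concern.** A rule that ends dosing in an individual patient should give the same answer wherever a site looks it up. Here the section that a site opens when an abnormal result arrives (3.4.4.2) gives a milder instruction than the section that lists the permanent stops (4.7), for essentially the same finding. The cross-reference that should tie them together leads to a rule that is not there.

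The main stake is patient safety: further infusions in someone whom the protocol elsewhere takes off drug. It also touches the primary objective, because permanent discontinuation is part of how tolerability is judged.

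**Working it through.** The plan states no figure to reproduce. The check sets the two sections side by side, follows one patient through both, and counts the doses affected.

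**Comparison**

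| | Section 3.4.4.2 | Section 4.7 |
|---|---|---|
| ALT/AST permanent stop | 3 missed doses in a row, cites 4.7 | 3 missed doses in a row |
| Bilirubin permanent stop | 2 missed doses in a row, cites 4.7 | two consecutive values > 2 × ULN, at least 1 week apart |
| Gilbert's/hemolysis exclusion | on the hold after the repeat, not on the stop | on the stop |

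The transaminase row agrees and the bilirubin row does not. The same form of cross-reference works for one and fails for the other, which suggests that the sections were meant to correspond.

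**One patient through both sections** (bilirubin values assumed for illustration; neither Gilbert's syndrome nor hemolysis)

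1. Day 14: 2.5 × ULN. Immediate repeat, about Day 15: 2.4 × ULN. One-week repeat, about Day 22: 2.3 × ULN.
2. Section 4.7: consecutive values at least a week apart are above 2 × ULN, so no further drug from about Day 22, before any dose has been missed.
3. Section 3.4.4.2: withhold the Day 28 dose. One dose is missed, so the two-dose stop is not reached.
4. Day 28 sample below ULN. A site reading 3.4.4.2 alone would see dosing as permitted on Day 42. Section 4.7 bars it.

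From the first high value, the earliest permanent stop is about 7 days under 4.7. Under the 3.4.4.2 missed-dose rule it is 28 days, when the second of two fortnightly doses is missed.

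**Doses at issue.** Dosing days are 0, 14, …, 182. If the first high value is on day *d*, the dose on *d* + 14 is missed under either section. The upper bound on doses given under 3.4.4.2 but barred by 4.7 is the number of visits from *d* + 28 to 182:

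(182 − (*d* + 28)) / 14 + 1

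- *d* = 14: (182 − 42) / 14 + 1 = 11
- *d* = 56: (182 − 84) / 14 + 1 = 8
- *d* = 98: (182 − 126) / 14 + 1 = 5
- *d* = 154: (182 − 182) / 14 + 1 = 1

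These are maxima. They assume that bilirubin normalises in time for the second visit and that nobody consults 4.7 or intervenes. Day 14 is used as the earliest on-treatment value because the Day 0 sample is drawn before the first infusion (Table 4, footnotes c and j).

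**Exclusion.** The opening hold in 3.4.4.2 applies to any value above 2 × ULN. A patient with Gilbert's syndrome who stays above that level has no branch after the repeat. If doses go on being held, that patient meets the missed-dose stop, which has no exclusion. The bilirubin entry in 4.7 deliberately leaves the same patient out.

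**Frequency.** No rate of bilirubin above 2 × ULN is given. Section 1.5 names only headache as an adverse event above 10% among 51 dosed patients, so a bilirubin adverse event would have been recorded in at most 5 (10% of 51 = 5.1). That bounds recorded events, not laboratory values.

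**The case against.** The strongest reply is that these are two sufficient triggers and either one stops drug. Section 3.4.4.2 does not say that two missed doses are the sole ground, and 4.7 applies if any listed event occurs. A permission to resume does not override a prohibition. Nor is the hold in 3.4.4.2 empty on that reading: values of 2.5, then 1.8 at the immediate repeat, then 2.1 × ULN at one week leave the patient above 2 × ULN without two consecutive high values a week apart, so only the hold applies. It can also be said that the three results in 3.4.4.2 are alternatives on one repeat test, and nothing expressly moves a patient from the first to the second.

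Most of this stands, and it limits the point. A reader might infer that a site could follow either section and be compliant both times. The text does not support that: a site that resumes drug after the 4.7 entry is met has broken 4.7. What the reply does not remove is that 3.4.4.2 tells the site what to do with a value still high at one week, gives only a withheld dose, and refers to a stop that 4.7 does not contain.

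A reader might also see a conflict in the other direction: repeats between ULN and 2 × ULN, held for two doses, stopped under 3.4.4.2 but not under the 4.7 bilirubin entry. That is not a contradiction. Section 4.7 lists reasons to stop and authorises no dosing. It is also not exhaustive, since Table 3 stops drug for a recurrent Grade 2 infusion reaction that 4.7 does not list. The patient has one outcome, with the medical monitor involved.

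**Conclusion.** The inconsistency is real and sits in current operative text. For consecutive values above 2 × ULN at least a week apart, without Gilbert's syndrome or hemolysis, 4.7 requires that drug end, while 3.4.4.2 directs only that the next dose be withheld and relies on a cross-reference that fails. A site working from 3.4.4.2 could re-dose a patient whom 4.7 bars, by at most 11 doses for a first on-treatment high value at Day 14 and fewer later. The missing exclusion on the 3.4.4.2 stop is a smaller, separate gap.

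Two larger claims are tempting and should not be made. Counting from Day 0 would give 12 doses, but that sample precedes treatment. One might also argue that the choice of section changes who counts as evaluable. That depends on reading the first four doses in Section 2.4.1 as the four scheduled for Days 0 to 42, which the protocol does not state.

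The safety analyses include all patients either way, so adverse event capture is unaffected. The number of patients concerned is unknown and probably small. The point merits consideration as a correction to a patient-level safety rule.

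**What to change.** Align 3.4.4.2 to 4.7 with three edits:

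1. In 3.4.4.2, where bilirubin is still above 2 × ULN at the one-week repeat and the 4.7 criterion is met, replace the instruction to skip the next dose with an instruction to discontinue study drug under Section 4.7.
2. Add the stop for two successive missed doses due to bilirubin to the 4.7 list, so that the cross-reference holds.
3. State in both sections whether the Gilbert's/hemolysis exclusion applies to the missed-dose stop.

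The cost is a few sentences in an amendment, with no new tests or visits. The clinical price is that some patients whose bilirubin would have normalised by the second visit come off drug; 4.7 already requires that.
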